### **5.3.6 Metabolic Tumor Imaging**

Under the direction of [name], special research analyses/readings of standard 18F-FDG PETs collected per standard of care will be performed to evaluate metabolic tumor volume and total lesion glycolysis.

### **5.3.7 DNA Copy Number Analysis**

Array comparative genomic hybridization (e.g., on Agilent 240K or Affy SNP 6.0 microarrays) will be used to assess DNA copy number alterations as described, in tumor DNA to yield somatically acquired regions of copy number gain and loss.

### **5.3.8 Pharmacokinetics (PK) and Anti-drug Antibodies (ADA) Analysis**

Validated assays will be used to measure magrolimab serum concentration and presence of anti-magrolimab antibodies. Coded (linked) samples (Section [5.4.2](#)) will be sent to a contracted laboratory at the request of Gilead Sciences, Inc. for analysis of magrolimab pharmacokinetics and presence of anti-magrolimab antibodies: PPD Laboratories.

PPD will run validated assays to measure magrolimab serum concentration and presence of anti-magrolimab antibodies. See [Appendix F](#) for additional details.

The laboratory contact information is as follows:

### 5.3.9 Other Analyses

Other analyses include the following:

- Cell analysis and histological (e.g., H&E), immunohistochemical review and analysis per standard and established research techniques (e.g., PD-1/PD-L1 expression [Dako], FISH for 9p24 amplicon, and other IHC analyses in blood and tissue).
- Cytokine analysis (e.g., IL-6, IL-10, interferon beta, TNF-alpha)
- cfDNA/ctDNA for liquid genotyping as a non-invasive dynamic monitoring of disease as well as monitoring for individual molecular aberrations that herald progression or disease transformation; specifically, amplification and sequencing of the VDJ segment of the immunoglobulin receptor is planned

### 5.3.10 Future Use

Any blood, tissue, or other (e.g., CSF) products or portions leftover from other analyses will be stored for future research.

## 5.4 SAMPLE STORAGE, TRACKING AND DISPOSITION

### 5.4.1 General

Samples will be ordered in CRIS and tracked through a Clinical Trial Data Management system. Should a CRIS screen not be available, the CRIS downtime procedures will be followed. Samples will not be sent outside NIH without appropriate approvals and/or agreements, if required.

All specimens obtained in the protocol are used as defined in the protocol. Any specimens that are remaining at the completion of the protocol will be stored in the conditions described below. The study will remain open so long as sample or data analysis continues. Samples from consenting patients will be stored until they are no longer of scientific value or if a subject withdraws consent for their continued use, at which time they will be destroyed. The PI will record any loss or unanticipated destruction of samples as a deviation. Reporting will be per the requirements of Section 7.2.

If the patient withdraws consent his/her data will be excluded from future distributions, but data that have already been distributed for approved research use will not be able to be retrieved.

### 5.4.2 Clinical Pharmacology Program ([name] Lab)

#### 5.4.2.1 Sample Data Collection

All samples sent to the Blood Processing Core (BPC) of the Clinical Pharmacology Program under the direction of [name] will be barcoded, with data entered and stored in the Labmatrix utilized by the BPC. This is a secure program, with access to Labmatrix limited to defined [name] lab personnel, who are issued individual user accounts. Installation of Labmatrix is limited to computers specified by [name]. These computers all have a password restricted login screen. All [name] lab personnel with access to patient information annually complete the NIH online Protection of Human Subjects course.

Labmatrix creates a unique barcode ID for every sample and sample box, which cannot be traced back to patients without Labmatrix access. The data recorded for each sample includes the patient ID, name, trial name/protocol number, time drawn, cycle time point, dose, material type, as well as box and freezer location. Patient demographics associated with the clinical center patient number are provided in the system. For each sample, there are notes associated with the processing method (delay in sample processing, storage conditions on the ward, etc.).

#### **5.4.2.2 Sample Storage**

Barcoded samples are stored in barcoded boxes in a locked freezers at appropriate temperatures (e.g., -20°C to -80°C) according to stability requirements. These freezers are located onsite in the BPC and offsite at NCI Frederick Central Repository Services in Frederick, MD. Visitors to the laboratory are required to be accompanied by laboratory staff at all times.

Access to stored clinical samples is restricted. Samples will be stored until requested by a researcher named on the protocol. All requests are monitored and tracked in Labmatrix. All researchers are required to sign a form stating that the samples are only to be used for research purposes associated with this trial (as per the IRB approved protocol) and that any unused samples must be returned to the BPC. It is the responsibility of the NCI Principal Investigator to ensure that the samples requested are being used in a manner consistent with IRB approval.

Sample barcodes are linked to patient demographics and limited clinical information. This information will only be provided to investigators listed on this protocol, via registered use of the Labmatrix. It is critical that the sample remains linked to patient information such as race, age, dates of diagnosis and death, and histological information about the tumor, in order to correlate genotype with these variables.

#### **5.4.3 Hematopathology Section of Laboratory of Pathology (Tissue samples)**

Archival and/or freshly collected and processed tumor tissue may be stored in the Hematopathology Section of Laboratory of Pathology until ready for planned and/or future research assays if the patient has agreed to allowing specimens to be used in future research studies. IRB approval will be obtained before using any samples to conduct studies that are not described within this protocol. Samples will be stored under conditions appropriate to the type of sample and processing (e.g., ambient or frozen).

Tissue that is given to the technician will be assigned an accession number (HP#) in the HP Case Log book; sample tracking also takes place with a FileMaker Pro data base called HP Patient Information and Specimen Inventory. A Patient background sheet may be filled out and filed with any accompanying paperwork, with final reports and any supplemental reports that follow added as completed.

#### **5.4.4 [name] Lab**

##### **5.4.4.1 Sample Data Collection**

Patient samples, collected for research under this IRB approved protocol, may be archived in the [name] laboratory. All data associated with archived clinical research samples is entered into the web-based NCI Labmatrix database, a centralized system with access controlled via centralized login. Access to this database for samples collected from this study is limited to [name] and his research staff, each requiring individual login and password. All staff in the laboratory receive annually updated NIH/CITI or other training, as appropriate, and maintain standards of computer security.

The data recorded for each sample may include the patient ID, trial name/protocol number, date drawn/collected, treatment cycle/time point, sample source (e.g., peripheral blood, marrow, tissue, etc.) as well as box and freezer location. All received samples will be given a unique bar code number, which will be added to the sample NCI Labmatrix database. Only this bar code will be recorded on the sample vial and the vials will not be traceable back to patients without authorized access to the NCI Labmatrix database.

#### **5.4.4.2 Sample Storage**

Samples are stored in freezers at -80°C (e.g., sera, plasma, tissue samples) or under liquid nitrogen (e.g., cells), according to established stability requirements. These freezers are located onsite under the direction of [name]. Access to samples from this protocol for research purposes will be as outlined in this protocol or by permission of the Principal Investigator only.

#### **5.4.5 Nuclear Medicine/Tumor Imaging ([name])**

As [name] is also a clinical nuclear medicine clinician reading the images also for standard of care, he will have access to identifiers of the subjects; however, his assessments specifically for the research metabolic tumor imaging analyses will not be recorded in the medical record, but only in the research records similar to other research-specific data and results.

#### **5.4.6 CAT-I Laboratory ([name] Lab)**

The CAT-I laboratory (CAT-I) will obtain coded samples from [name] and his staff. Upon sample acquisition, members of the CAT-I laboratory will enter these samples into CEREBRO, an advanced sample labeling system that tracks each sample through every step of the workflow. To meet requirements for availability of primary data and for quality assurance checks, CAT-I will maintain a detailed inventory of the type (slide, tissue, frozen OCT block) and location of each sample in the laboratory. More specifically, frozen OCT blocks and accompanying slides will be physically stored in the CAT-I laboratory. Tissues provided will be fixed, frozen, and stored in the CAT-I's -80°C freezer. The CAT-I laboratory will be locked when CAT-I lab members are not present. Unprocessed samples will be held by the CAT-I or returned upon their request. Finally, the CAT-I will comply with requirements for annual Biospecimen Reporting at the NIH.

### **5.5 SAMPLES FOR GENETIC/GENOMIC ANALYSIS**

#### **5.5.1 Description of the scope of genetic/genomic analysis**

The research correlates for this study are expected to include DNA/RNA sequencing of tumors, including circulating tumor DNA. In addition, whole exome sequencing may include evaluation for known lymphoma mutations. For any genetic studies performed, the results will be deposited in a database such as dbGaP per NIH requirements. Although there is controlled access to such a database, such a submission carries theoretical risks of revealing the identity of the subject. This is discussed in the consent.

#### **5.5.2 Description of how privacy and confidentiality of medical information/biological specimens will be maximized**

Confidentiality for genetic samples will be maintained as described (Section 5.4). In addition, a Certificate of Confidentiality has been obtained for this study.

### **5.5.3 Management of Results**

Subjects will be contacted if a clinically actionable gene variant is discovered. Clinically actionable findings for this study are defined as disorders appearing in the American College of Medical Genetics and Genomics recommendations for the return of incidental findings that is current at the time of primary analysis. (A list of current guidelines is maintained on the CCR intranet: <https://ccrod.cancer.gov/confluence/display/CCRCRO/Incidental+Findings+Lists>).

### **5.5.4 Genetic Counseling**

Subjects will be contacted with a request to provide a sample to be sent to a CLIA certified laboratory. If the research findings are verified in the CLIA certified lab, the subject will be offered the opportunity to come to NIH to have genetic education and counseling to explain this result; at the time of any such event(s), these activities will be funded by the NCI/CCR in consideration of the specific circumstances. If the subject does not want to come to NIH, a referral to a local genetic healthcare provider will be provided (at their expense).

This is the only time during the course of the study that incidental findings will be returned. No interrogations regarding clinically actionable findings will be made after the primary analysis.

## **6 DATA COLLECTION AND EVALUATION**

### **6.1 DATA COLLECTION**

#### **6.1.1 Summary**

The PI will be responsible for overseeing entry of data into a 21 CFR Part 11 compliant data capture system provided by the NCI CCR and ensuring data accuracy, consistency and timeliness. The principal investigator, associate investigators/research nurses and/or a contracted data manager will assist with the data management efforts. Primary and final analyzed data will have identifiers so that research data can be attributed to an individual human subject participant.

All adverse events, including clinically significant abnormal findings on laboratory evaluations, regardless of severity, will be followed until return to baseline or stabilization of event.

Document AEs from the first study intervention, Day 1 through 30 days after the last dose of study agent was administered. Beyond the 30 day period after the last drug was administered, only adverse events which are serious and related to the study intervention need to be recorded.

**End of study procedures:** Data will be stored according to HHS, FDA regulations, and NIH Intramural Records Retention Schedule as applicable.

**Loss or destruction of data:** Should we become aware that a major breach in our plan to protect subject confidentiality and trial data has occurred, this will be reported expeditiously per requirements in Section [7.2.1](#).

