#### **3.7.1 30-Day Safety Follow-Up visit**

The mandatory Safety Follow-Up visit should be performed approximately 30 days following the last dose of study drug or before the first dose of new anti-cancer therapy, whichever comes first. Refer to the Study Calendar ([Appendix G](#)) for all tests and procedures to be conducted upon discontinuation of treatment and during follow-up. All AEs that occur prior to the safety follow-up visit should be recorded. See section [6.1.1](#) for documentation of AEs after study treatment has ended. The investigator or qualified designee will collect information about the new anti-neoplastic therapy initiated after the last dose of trial treatment. Once new anti-cancer therapy has been initiated the subject will move into survival follow-up.

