### **3.10 CRITERIA FOR REMOVAL FROM PROTOCOL THERAPY AND OFF STUDY CRITERIA**

A safety visit will occur 30 days post last dose of study drug. Prior to removal from study, effort must be made to have all patients complete an additional safety visit 18 months after the last dose of obinutuzumab as obinutuzumab has the longest half-life out of the experimental drugs for this study. Details of additional safety visits and follow-up will continue as per Section [3.7](#).

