### **8.1.6 Adverse Events of Special Interest (AESI)**

There are no AESI with respect to the NCI CCR Sponsor representative for this protocol.

AESI for the pharmaceutical collaborator, Genentech, include the following:

- Cases of potential drug-induced liver injury that include an elevated ALT or AST in combination with either an elevated bilirubin or clinical jaundice, as defined by Hy's law:

- Treatment-emergent ALT or AST > 3 x ULN in combination with total bilirubin > 2 x ULN
- Treatment-emergent ALT or AST > 3 x ULN in combination with clinical jaundice
- Data related to a suspected transmission of an infectious agent by the study drug (STIAMP), as defined below:
- Any organism, virus, or infectious particle (e.g., prion protein transmitting transmissible spongiform encephalopathy), pathogenic or non-pathogenic, is considered an infectious agent. A transmission of an infectious agent may be suspected from clinical symptoms or laboratory findings that indicate an infection in a patient exposed to a medicinal product. This term applies only when a contamination of the study drug is suspected.

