##### 8.1.6.1.1 Obinutuzumab-specific AESI

- All Tumor Lysis Syndrome (irrespective of seriousness, causality or severity)
- Second Malignancies

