|---|------------------------|---|-----------------------------|------------|--|------------------------|---|--------------|-----------------------------------|---|----------------------------------|-----------------------------|
|   |                        |   | C -2
D1                  | C -1
D1 | C1-C6
D1                              | C7-C12
D1           | Window C-1/
Pre-C1,
Cycles 6 & 12     | Cycles 3 & 9 |                                   | Safety (Day 30)                           | Follow-Up (Prior to PD)          | Survival (Post-PD)          |
| Scheduling Window (Days):   | -28 to -1  | -28 
-14* or -7 ^ | -3                          | -3         | -3                                       | -3                     | Last 7 days of the cycle                    |              | Treatment discon./PD  | +7  | Every 3 or 6 months  | Every 3 months  |
| Bone Marrow Aspiration (with flow cytometry)/ Biopsy                     | X                      |   |                             |            |  | X                      |   |              | X                                 |   |                                  |                             |
| CT Scans or MRI    | X                      | X   |                             |            |  |                        | X   | X            | X                                 |   | X                                |                             |
|  F-FDG-PET/CT Scan    |                        | X   |                             | X          |  |                        | X   |              | X                                 |   |                                  |                             |
| Symptoms/Adverse Events, Concomitant Medication Reviews                               | X                      | X   | X                           | X          | X  | X                      |   |              | X                                 | X   |                                  |                             |
| Research Tissues (archival/fresh biopsy, bone marrow biopsy/aspiration)  |                        |   |                             |            |  |                        | See Research Sample Calendar in Section 5.1 |              |                                   |   |                                  |                             |

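### The post-30-day recording rule for adverse events, limited to serious and related events, is not reconciled with the second-malignancy AESI, the SAE reporting sections, the 18-month safety visit or the study calendar

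*Combined protocol and SAP*

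**What the plan says.** **Recording rule.** Section 6.1.1: "Document AEs from the first study intervention, Day 1 through 30 days after the last dose of study agent was administered". After that, "only adverse events which are serious and related to the study intervention need to be recorded". Section 3.7.1 sends the reader to 6.1.1 "for documentation of AEs after study treatment has ended", so this is the operative post-treatment rule. Section 8.1.5 makes relatedness a two-way judgement, related or not related.

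**AEs of special interest (AESI).** Section 8.1.6 states: "There are no AESI with respect to the NCI CCR Sponsor representative for this protocol". The lists that follow belong to a pharmaceutical collaborator. The obinutuzumab list in 8.1.6.1.1 has two entries: "All Tumor Lysis Syndrome (irrespective of seriousness, causality or severity)" and "Second Malignancies". The second carries no qualifier of any kind.

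**Reporting.** Section 8.3 requires submission within 24 hours of serious adverse events (SAEs), and of AESIs that need expedited reporting. It states no causality condition and no end date. Section 8.2 refers back to 6.1 for the recording time frame. Section 8.5 leaves reporting to the collaborators to agreements outside the protocol.

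**Late visit.** Section 3.10: "effort must be made to have all patients complete an additional safety visit 18 months after the last dose of obinutuzumab". The reason given is the drug's half-life, and details are deferred to 3.7. Section 3.7 describes no such visit.

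**Calendar.** In Appendix G the row "Symptoms/Adverse Events, Concomitant Medication Reviews" is marked through End of Treatment or PD and the Day 30 safety visit. It is blank under Follow-Up (Prior to PD) and Survival (Post-PD). There is no 18-month column.

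**Analysis.** Section 10.4.4 says toxicities and SAEs will be reported, without separating on-treatment from late events.

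**The concern.** The primary objective is safety, in a single-arm, open-label trial of time-limited treatment. Patients in complete response (for CLL, with undetectable MRD as well) stop after 6 triplet cycles, while follow-up visits are scheduled for 5 years. Much of the observation time is therefore off drug.

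In that period a case reaches the AE data, as a minimum, only if the investigator calls it both serious and related. With no control arm, relatedness of a late second cancer rests on individual judgement. A count that depends on that judgement is not a count of second malignancies, and a low figure could not be interpreted. The SAE count under 10.4.4 would also change definition at day 30 without saying so.

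The sections can also be read in different ways. Staff following 6.1.1 and staff following 8.3 could treat the same unrelated second malignancy differently, and nothing says what AE information the 18-month visit should collect.

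**Working it through.** The plan states no expected rate or precision target for late events, so there is no figure of its own to reproduce here. Its planned size does reproduce: 24 dose-finding + 42 expansion = 66 treated patients (10.2).

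**1. The passages side by side: a second malignancy 12 months after the last dose, judged unrelated**

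| Section | Must it be recorded or reported? |
|---|---|
| 6.1.1 | No, because it fails the related condition |
| 8.1.6.1.1 | It is an AESI; no causality condition is given |
| 8.3 | Reportable if it is serious or an AESI needing expedited reporting; no causality limit |
| 8.2 | Recording time frame goes back to 6.1, so back to the first row |
| 3.10 | A later safety visit should be attempted; content undefined |
| Appendix G | No AE entry in Follow-Up or Survival |

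The sections give different answers and none is stated to prevail.

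**2. How much of the period to the 18-month visit is filtered**

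Inputs:
- Period T, from the last obinutuzumab dose (3.10): 18 x 365.25/12 = 547.875, about 548 days.
- Full recording runs to 30 days after the last dose of study agent (6.1.1).
- Lag L from last obinutuzumab to last study agent: 0 if they coincide, or 27 days if venetoclax runs to Day 28 of a cycle with obinutuzumab on Day 1 (Tables 11 and 12).

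Formula: filtered days = T - (L + 30); share = filtered days / T.

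- L = 0: 547.875 - 30 = 517.875, about 518 days (17.0 months); share 94.5%.
- L = 27: 547.875 - 57 = 490.875, about 491 days (16.1 months); share 89.6%.

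These are shares of calendar time, not of events.

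**3. Illustration of what the filter could do to a count**

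The documents give neither input, so both are assumptions: 18-month incidence p of second malignancy of 2%, 5% or 10%, and a fraction q of cases judged both serious and related of 10% to 50%. All n = 66 patients are taken as observed and all cases as falling in the filtered period. Expected cases = n x p; expected under the filter = n x p x q; P(at least one recorded) = 1 - (1 - pq)^n, with q = 1 for no filter.

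| p | Expected, no filter | Expected, filter | P(at least one), no filter | P(at least one), filter |
|---|---|---|---|---|
| 2% | 1.3 | 0.13-0.66 | 0.74 | 0.12-0.49 |
| 5% | 3.3 | 0.33-1.65 | 0.97 | 0.28-0.81 |
| 10% | 6.6 | 0.66-3.3 | 0.999 | 0.49-0.97 |

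For example, at p = 5%: 1 - 0.95^66 = 0.97; with q = 10%, 1 - 0.995^66 = 0.28; with q = 50%, 1 - 0.975^66 = 0.81.

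**4. Does the existing schedule reach month 18?**

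Follow-up before progression is three-monthly for two years, counted from the end of therapy, within 2 weeks either way (Appendix G, footnote 4). With L = 0 its month-18 visit coincides with the 3.10 visit. With L = 27 it falls at 27 + 548 = 575 days after the last obinutuzumab dose, at the earliest day 561. That is 13 days past the 18-month mark, so one visit can serve both purposes if the label carries a suitable window.

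**The case against.** Several stronger readings are tempting, and the documents do not support them.

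- **That late safety is largely lost, or that an unrelated second cancer has no place in the data.** Serious related events are recorded without time limit, and the threshold for related is only a reasonable possibility. Deaths are captured through survival follow-up. Follow-up visits before progression include history, examination, blood counts, chemistry, immunoglobulins and CT. Footnote 3 of Appendix G repeats the end-of-treatment assessments, whose column includes AE review, at progression or before new anti-cancer therapy. Section 6.1.1 sets a minimum and does not forbid recording more.
- **That the 18-month visit is mandatory.** Section 3.10 asks for effort only.
- **That the sponsor breaches its own AESI list.** The list is the collaborator's. The agreements mentioned in 8.5 may require late reporting regardless of causality, but they are not available to check.
- **That the cited fatal-event figures show late loss.** The 11.9% against 4.0% (MZL against FL) comes from obinutuzumab with chemotherapy; the protocol calls the infection risk in chemotherapy-free combinations unknown. The 4 infection deaths among 5 fatal AEs with venetoclax-obinutuzumab occurred during treatment, when 6.1.1 records everything.
- **That the primary analysis is biased.** It describes dose-limiting toxicities to the triplet, assessed in Cycle 1, and no late-event rate is separately planned.

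All of this limits the scope and stands. It does not settle the conflict. The reporting route in 8.3 depends on 8.2, which returns to 6.1. A review at progression still operates under 6.1.1 as to what must be recorded. Information in visit notes is not the same as a systematic AE record.

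**Conclusion.** The point holds as an unreconciled recording rule. After day 30, a second malignancy or serious late event judged unrelated need not be recorded under 6.1.1, while 8.1.6.1.1, 8.3 and 3.10 suggest that at least some such events are wanted. About 90-95% of the time to the 18-month visit is under the filter, assuming the last study-agent dose falls 0 to 27 days after the last obinutuzumab dose. If other study drugs continue longer after obinutuzumab stops, the share is lower.

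The textual conflict is certain. Its effect on the late event count is not: that depends on incidence and attribution rates the documents do not give, and on agreements not seen. The Cycle 1 dose-limiting toxicity analysis and AE recording through day 30 are untouched. This should be corrected as an inexpensive improvement to late safety reporting; it is not a flaw in the trial's main result.

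**What to change.** - **6.1.1:** record second malignancies regardless of causality through the end of follow-up. Record SAEs regardless of causality until the 18-month post-obinutuzumab visit or the start of new anti-lymphoma therapy, whichever is first. Keep the present rule for other late events.
- **8.2 and 8.3:** keep the reference to 6.1, so that the revised rule governs both recording and reporting.
- **3.7 and Appendix G:** label the 18-month visit, with a window that lets the nearest three-monthly visit serve for progression-free patients, and add an AE entry to the Follow-Up column.
- **10.4.4:** report events after day 30 separately from those up to day 30, stating the recording rule that applied.

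Routine collection of all late grade 3 or higher infections is not needed for this correction; serious infections would come in through the SAE rule.

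The cost is extra data entry at visits that already take place for progression-free patients. After progression or new therapy, patients are contacted only for survival, so a brief second-malignancy question must be added to those contacts. The late event count may look less favourable. No treatment changes.
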